**Figure 3. Effects of NT—I7 on absolute lymphocyte counts, proliferation rates, and CD4+ and CD8+ T-cell subsets.**

#### 2.3.2.2 Completed Study GX-I7-CA-003

GA- I7-CA-003 was a Phase 1b, single-agent, open-label, 3+3 dose-escalation study to determine the Recommended Phase 2 Dose (RP2D) and to evaluate safety, tolerability, PK, and pharmacodynamics of NT-I7 in subjects with locally advanced or metastatic solid tumors. GX-I7 (an alternative name for NT-I7) was administered IM on Day 1 of each 21-day cycle at doses of 60  $\mu$ g/kg, 120  $\mu$ g/kg, 240  $\mu$ g/kg, 480  $\mu$ g/kg, 720  $\mu$ g/kg, 960  $\mu$ g/kg, 1200  $\mu$ g/kg, and 1700  $\mu$ g/kg.

Pharmacodynamic data from the study showed ALC and naïve/less differentiated memory subsets of CD4+ and CD8+ T cells increased in a dose-dependent manner after NT-I7 administration. T cell increases were most prominent in the 1200  $\mu$ g/kg and 1700  $\mu$ g/kg dose groups. The levels of endogenous IL-7 remained at normal levels without any significant change.

The dose-dependent increase in exposure with GX-I7 was observed in all dose groups. Following IM administration, the GX-I7  $T_{max}$  was 11 to 47.5 hours depending on dose, with an elimination half-life of 60.8 to 139.7 hours.  $C_{max}$  and  $AUC_{last}$  increased with increasing dose of study drug, and both increased in a dose-proportional manner.

In GX-I7-CA-003, immunogenicity was assessed by measuring ADAs and nAb on all subjects. No subject was positive 8 days after the first administration of NT-I7, and ADAs and nAb were detected in all subjects by the third administration of NT-I7 (regardless of dose or dosing

interval). All subjects remained positive for both while continuing to receive NT-I7. Endogenous IL-7 levels were maintained at normal levels without significant change, and there were no specific AEs related to ADA. The presence of ADAs did not appear to affect drug exposure, pharmacodynamic endpoints, or safety of the drug with repeated dosing in patients with solid cancers.

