**5.4 N/A**

## 5.5 Biomarker plan

**Table 7. List of Biomarker Assays in Order of Priority**

Priority	Biomarker Name	Assay (CLIA: Y/N)	Use in the Trial and Purpose	Specimens Tested	Collection Time Points	Mandatory (M) or Optional (O)	Assay Laboratory
Tissue-based Biomarkers							
1	TCR Clonality	ImmunoSeq CLIA: N	Integrated Pharmacodynamics	KS biopsies	Baseline (week 0), week 9 or EOT, additional time point at week 13 is optional.	M (W0; W9 or EOT) O (W13)	Adaptive Biotechnologies
1	CD3, CD8, CD4, CD79A CD68, PD-1, FoxP3 and MHC Class I	Multi-Spectral IHC CLIA: N	Exploratory Pharmacodynamics	KS biopsies	Baseline (week 0), week 9 or EOT, additional time point at week 13 is optional.	M (W0; W9 or EOT) O (W13)	Fred Hutch Experimental Pathology
1	Gene Expression Profiling  Interferon $\gamma$ (INF $\gamma$ ) Gene Expression Signature	Nanostring nCounter $^{\circledR}$ PanCancer ThePanCancer IO 360 $^{\text{TM}}$  Additional add-in probes for genes that define the KSHV function  CLIA: N	Exploratory Pharmacodynamics	KS biopsies	Baseline (week 0), week 9 or EOT	M	Fred Hutch Molecular Core and Collaboration with NanoString $^{\circledR}$ Technologies

Priority	Biomarker Name	Assay (CLIA: Y/N)	Use in the Trial and Purpose	Specimens Tested	Collection Time Points	Mandatory or Optional	Assay Laboratory a
Blood-based Biomarkers							
1	Absolute lymphocyte count	CBC CLIA: Y	Integral Dosing considerations	PBMC (EDTA)	Baseline (week 0), week 1, week 4, week 9 (before second dose), week 13, week 18	M	CLIA Certified Site Laboratory
2	CD4+ and CD8+ T-cell counts	Flow Cytometry CLIA: Y	Integrated Pharmacodynamics	PBMC	Baseline (week 0), week 1, weeks 4, week 9 (before second dose), week 18, week 27	M	CLIA Certified Site Laboratory
1	ADA and NADA	ELISA CLIA: N	Integrated Dosing Considerations	Serum	Baseline (week 0), week 9; week 18; week 27; EOT	M	BioAgilytix
2	Whole Blood Immunophenotyping	Flow Cytometry CLIA: N	Exploratory Pharmacodynamics	Whole blood and PBMC	Baseline (week 0), week 1, week 4, week 9 (before second dose), week 18, week 27	O	CITN Central Immune Monitoring Lab (CIML) [name] [contact]

Priority	Biomarker Name	Assay (CLIA: Y/N)	Use in the Trial and Purpose	Specimens Tested	Collection Time Points	Mandatory or Optional	Assay Laboratory a
Blood-based Biomarkers (cont.)							

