## 9.2 Sample Size/Accrual Rate

Two participants at minimum and a maximum of 6 participants at each dose level will be treated. Up to 2 participants who do not complete at least one year of follow up for reasons other than toxicity or disease progression may be replaced. Up to twenty patients will be enrolled in the study.

This protocol is designed to meet clinical needs of women and members of minority groups. The planned enrollment report (below) is based on US HIV demographics and previous studies.

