#### 9.4.3 Kinetics of CD4+ and CD8+ T cells in blood, and on levels and phenotype within tumors, using flow cytometry and immunohistochemistry, respectively.

It is hypothesized that NT-I7 will lead to T cell expansion over the first 4-8 weeks after administration and that increases will be measurable in the blood using total blood counts with automated differentials and flow cytometry and in tumors by immunohistochemistry at 9 weeks. For blood measurements, ALC will be measured primarily, while absolute CD4+ and CD8+ T cell will be evaluated secondarily. Tumor infiltrating lymphocytes (TILs) will be evaluated quantitatively (cells/hpf) with qualitative annotation of the pattern of distribution.

For analysis of circulating lymphocytes we will first describe fold-change (median and range) in blood ALC from pre-administration to each time point following first administration (1, 4, and 9 weeks), and by category of selected participant characteristics (e.g., dose level, age [by decade], sex, HIV status, prior systemic therapy, and in HIV+, by CD4+ T cells (< versus  $\geq$  200 cells/uL). More formally, we will explore multilevel negative binomial regression to estimate fold-change from pre-administration, adjusted for NT-I7 dose, HIV status, prior therapy, and baseline CD4+ T cell counts. In this analysis, ALC is the dependent variable and a generalized linear mixed model is applied with time from administration (weeks), an indicator of first or second administration, and gap between first and second administration as independent variables of interest in addition to adjustment variables. A random intercept is included for each participant to incorporate correlation between T cell counts from the same participant. The exponentiated fixed-effects model coefficients estimate fold-change from baseline with 95% CIs for a representative participant.

The same analytic approach will be applied to analysis of CD4+ and CD8+ T cells separately, and to TIL counts.

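### With only a random intercept per participant, the T-cell kinetics model gives 95% CIs for the week-4 fold-change that are too narrow if participants expand by different amounts

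*Combined protocol and SAP*

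**What the plan says.** Section 9.4.3 begins with a descriptive step: median and range of the fold-change in ALC at weeks 1, 4 and 9 after the first dose, overall and by dose level, HIV status and other characteristics. It continues: "More formally, we will explore multilevel negative binomial regression to estimate fold-change from pre-administration". The model is a generalized linear mixed model "with time from administration (weeks), an indicator of first or second administration, and gap between first and second administration as independent variables of interest". NT-I7 dose, HIV status, prior therapy and baseline CD4+ count are adjustment variables.

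The participant-level structure is one sentence: "A random intercept is included for each participant to incorporate correlation between T cell counts from the same participant". The reported result is stated as follows: "The exponentiated fixed-effects model coefficients estimate fold-change from baseline with 95% CIs for a representative participant". The same approach is to be used for CD4+, CD8+ and TIL counts. The section names no random effect for post-dose change, dose-by-time term, robust variance or small-sample correction.

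Table 7 in section 5.5 schedules ALC at "Baseline (week 0), week 1, week 4, week 9 (before second dose), week 13, week 18". On size, section 9.2 says: "Up to twenty patients will be enrolled in the study". It allows at most six participants per dose level. Section 2.3.2.2 reports that in the earlier solid-tumor study ALC and T-cell subsets "increased in a dose-dependent manner after NT-I7".

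**The concern.** A random intercept lets participants differ in their level of ALC, not in how much ALC changes after dosing. The adjustment variables also shift only the level, because none is interacted with time. Given the covariates, every participant is assumed to have the same true fold-change.

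If that is untrue, the differences in expansion go into the residual (dispersion) term. The model treats that term as independent from visit to visit and averages it over all visits. A participant who expands strongly at week 4 is then read as having a noisy visit. For contrasts at the time of greatest divergence, the standard error comes out too small.

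Objective 1.2.4, the kinetics of ALC, CD4+ and CD8+ cells, is a named secondary objective. These are the only confidence intervals the plan provides for it. Section 9.1.1.1 lists the ALC, CD4+ and CD8+ responses among the additional RP2D considerations, so intervals that overstate precision would be read in that setting.

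**Working it through.** **Plan's figure.** The only figure to reproduce is the nominal 95%. No SD, power or sample size is given for this analysis.

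**Inputs.**
- From the documents: ALC visits at weeks 0, 1, 4, 9, 13 and 18 (T = 6), and n = 12 and 18, both within the section 9.2 limits.
- Assumed: residual SD σ = 0.2 on the log scale; between-participant SD of log fold-change h = 0, 0.2, 0.4 or 0.6. These differences act with weight w = 0, 0, 1, 0.5, 1, 0.5 at the six visits (full four weeks after a dose, half at weeks 9 and 18).
- Time is taken as a factor, which removes any misfit from a straight line.

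For scale, section 2.3.2.1 reports a 111.4% ALC rise after 60 µg/kg IM, a 2.11-fold change. Taking that as the centre, h = 0.2 puts about two-thirds of participants between 2.11/e^0.2 = 1.7-fold and 2.11 × e^0.2 = 2.6-fold.

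**Formulas (log scale, balanced data).** The contrast of week k with week 0 is the mean of the within-participant differences.
- n × true variance = 2σ² + h²w_k²
- n × variance the model reports, on average = 2[σ² + h²S/(T−1)], where S = Σ(w − w̄)²
- R = true variance / model variance
- Large-sample coverage = 2Φ(1.96/√R) − 1

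Here w̄ = 3/6 = 0.5, S = 4 × 0.25 = 1 and S/(T−1) = 0.2. With 2σ² = 0.08, the model term is 0.08 + 0.4h².

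**Week 4 (w = 1).**

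| h | true | model | R | model SE / true SE | coverage, formula | coverage, simulated, n = 12-18 |
|---|---|---|---|---|---|---|
| 0 | 0.080 | 0.080 | 1.00 | 1.00 | 95% | 94-95% |
| 0.2 | 0.120 | 0.096 | 1.25 | 0.89 | 92.0% | 91-92% |
| 0.4 | 0.240 | 0.144 | 1.67 | 0.77 | 87.1% | 86% |
| 0.6 | 0.440 | 0.224 | 1.96 | 0.71 | 83.8% | 83% |

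The loss disappears at h = 0, which isolates the cause. R does not involve n, so more participants do not cure it.

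**Other contrasts, for h = 0.2, 0.4 and 0.6.**
- Week 9 (w = 0.5): R = 0.090/0.096, 0.120/0.144 and 0.170/0.224, giving 95.7%, 96.8% and 97.6% (simulated 95-97%).
- Week 1 (w = 0): R = 0.080/0.096, 0.080/0.144 and 0.080/0.224, giving 96.8%, 99.1% and 99.9% (simulated 96-99.8%). These intervals are too wide, not too narrow.

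**TIL.** Section 6.1.2 makes two biopsies mandatory. With T = 2 and w = (0, 1), S = 0.5, so the model term is 2σ² + h², equal to the true one, and R = 1 at every h. Simulated coverage with 1.96 limits is 92-94% at every h. That small shortfall comes from using z instead of t.

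**Sensitivity.**
- The negative binomial mixed model itself was fitted with visits at weeks 0, 1, 4 and 9, time as a factor, and heterogeneity half at week 1 and full at weeks 4 and 9. At n = 12, coverage was 88-91%, 84-86% and 83% for h = 0.2, 0.4 and 0.6. At n = 18 it was 92-93% and 88% for h = 0.2 and 0.4. With 300 replicates, Monte Carlo error is 1 to 2 points; at h = 0 and n = 12 coverage was 90-94%.
- In the log-scale model on those four visits, if a participant's deviations correlate only 0.5 across visits, coverage is 91-94%.

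**Remedies.** A t-interval on each participant's own log fold-change covers 95% at every h. In a linear-time check at n = 9 to 20, participant-level slopes (equivalent to a random slope in balanced data) with 1.96 limits covered only 91-94%; with t limits, 95%.

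**The case against.** The strongest case against has four parts.

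1. The model is introduced as exploratory and follows a descriptive median and range by time and dose level. The range shows between-participant spread directly. This stands, and it limits the consequence. It does not make the reported CIs right.

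2. Dose-dependence is a difference in means between doses. It belongs in a fixed dose-by-time term and says nothing about spread within a dose. This is correct: the documents give no within-dose SD of expansion. But the stated model has neither that term nor a random effect for change, so it cannot represent unequal expansion from either source. The section's own plan to describe fold-change by dose, HIV status and CD4+ stratum shows that variation is expected.

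3. Heterogeneity is not wholly ignored, since part of it inflates the dispersion term. This also stands. It is why weeks 1 and 9 can be covered at or above 95%. A reader might infer that every fold-change interval, including those for TIL, is too narrow; the working above does not support that.

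4. No RP2D rule uses these intervals. Section 6 selects from the MTD and the dose with maximum observed T-cell effects, with intratumor levels dominating. Section 9.1.1.1 caps the RP2D by DLTs. A reader might infer that the RP2D, or a dose comparison feeding it, rests on these CIs. It does not: without a dose-by-time term, the model yields no dose-specific fold-change interval.

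**Conclusion.** The concern holds in limited form. As specified, the model will understate uncertainty for ALC, CD4+ and CD8+ fold-changes at the on-treatment peak if participants expand by different amounts, and that is likely. In the illustration, week-4 coverage of a nominal 95% interval is about 91-92%, 86% or 83%.

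Those figures rest on assumed values: a residual SD of 0.2, an SD of log fold-change of 0.2 to 0.6, and divergence that peaks four weeks after a dose. A reader might take some such range as the trial's actual coverage. The documents do not support that, because they give neither SD, and other assumptions move the answer from about 95% down to about 60%. The low end needs a single straight line through all six visits, which is not the natural reading, since time from administration restarts at dose 2.

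The point affects the validity of secondary-endpoint intervals. It does not affect safety evaluation or dose escalation.

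**What to change.** For ALC, CD4+ and CD8+, make the main estimate in section 9.4.3 the mean of each participant's log fold-change from baseline at weeks 1, 4 and 9, overall and by dose level. Exponentiate it and give a t-interval. Keep the mixed model as supportive.

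Alternatively, keep the mixed model as the main analysis and add three things: a participant-level random effect for post-dose change (or a cluster-robust variance), a dose-by-time term, and t-type small-sample limits. A random slope with 1.96 limits is not enough. TIL counts from two biopsies need only t limits; where the optional week-13 biopsy adds a third observation, the same choice applies.

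The cost is a sentence or two in section 9.4.3, a little more analysis, and wider peak intervals. By-dose intervals will be very wide: with six participants there are 5 degrees of freedom, and with three only 2. Participants without a given visit drop out of that week's estimate, which is a reason to retain the mixed model as support. No new visits or samples are needed.

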#### 9.4.4 Immunogenicity of NT-I7 in participants with KS

The proportion of participants developing neutralizing antibodies will be summarized.

## 10. ADVERSE EVENTS: LIST AND REPORTING REQUIREMENTS

Adverse event (AE) monitoring and reporting is a routine part of every clinical trial. The following list of AEs ([Section 10.1.2](#)) and the characteristics of an observed AE ([Sections 10.2](#) and [10.3](#)) will determine whether the event requires expedited reporting via the CTEP Adverse Event Reporting System (CTEP-AERS) **in addition** to routine reporting.

### 10.1 Comprehensive Adverse Events and Potential Risks Lists(s) (CAEPRs): N/A

10.1.1 CAEPRs for CTEP IND Agent(s): N/A

10.1.2 Adverse Event List for NT-I7 (NSC 805638)

Data from two completed clinical studies and interim safety data from seven ongoing studies indicate that NT-I7 has been well tolerated with predominantly Grade 1 and Grade 2 AEs, two treatment-related Grade 4 AEs, and no Grade 5 AEs. Increases in ALC have been observed following treatment (after an initial decrease) with peak effect approximately three weeks after treatment.

10.1.2.1 Completed Study GX-I7-HV-001

A total of 58 treatment-emergent adverse events (TEAEs) were reported by 26 of 30 subjects (86.7%). In each NT-I7 treatment group, 8 of 8 subjects (100.0%) reported TEAEs compared with 2 of 6 subjects (33.3%) in the placebo group. The majority of TEAEs were mild in intensity. Most TEAEs were considered probably or possibly related to study drug. There were no serious TEAEs or TEAEs leading to death reported during the study.

All TEAEs had resolved by follow-up. The most frequent AEs were injection site reactions, headache, and productive cough. Injection site reactions were considered related to the study drug and were much milder after IM administration than after SQ administration. No other clinically significant abnormalities were found in clinical laboratory tests, vital signs, 12-lead electrocardiogram (ECG), or physical examinations. More details are provided in the NT-I7 Investigator's Brochure.

10.1.2.2 Completed Study GX-I7-CA-003

A total of 225 TEAEs occurred in 35 subjects (100.0%). By dose group, 14 TEAEs were reported in the NT-I7 60  $\mu$ g/kg group, 30 TEAEs in the NT-I7 120  $\mu$ g/kg group, 15 TEAEs in the NT-I7 240  $\mu$ g/kg group, 21 TEAEs in the NT-I7 480  $\mu$ g/kg group, 35 TEAEs in the NT-I7 720  $\mu$ g/kg group, 6 TEAEs in the NT-I7 960  $\mu$ g/kg group, 88 TEAEs in the NT-I7 1200  $\mu$ g/kg group, and 16 TEAEs in the 1700  $\mu$ g/kg group. When the severity of AEs was graded using the NCI-CTCAE (Version 4.0), 118 TEAEs were mild (Grade 1), 84 TEAEs were moderate (Grade 2), 16 TEAEs were severe (Grade 3), and 4 TEAEs were life-threatening or required urgent intervention (Grade 4). Three TEAEs were reported as death related to AEs (Grade 5). During the study, there were 3

subjects who experienced 4 SAEs that resulted in death. All deaths were considered not related to NT-I7.

By preferred term (PT), the most common AEs were injection site reactions (61 TEAEs in 25 subjects [71.4%]), pyrexia (26 TEAEs in 15 subjects [42.9%]), and abdominal pain (10 TEAEs in 10 subjects [28.6%]).

There were 6 SAEs in 5 subjects (14.29%): 1 subject in the 120  $\mu\text{g}/\text{kg}$  group had Grade 5 mesenteric arterial occlusion (not related to NT-I7); 1 subject in the 480  $\mu\text{g}/\text{kg}$  group had Grade 3 ascites and Grade 5 upper gastrointestinal hemorrhage (both not related); 2 subjects in the 1200  $\mu\text{g}/\text{kg}$  group had Grade 2 azotemia and Grade 5 dyspnea (both not related); and 1 subject in the 1700  $\mu\text{g}/\text{kg}$  group had Grade 3 hypersensitivity (related). The last event was also a serious ADR.

Adverse drug reactions were AEs that could not be completely excluded from relationship to study drug. A total of 116 ADRs occurred in 28 of 35 subjects (80.0%). All of the ADRs were determined to be related to study drug. By dose group, 3 subjects (100.0%, 6 events) reported ADRs in the NT-I7 60  $\mu\text{g}/\text{kg}$  group, 2 subjects (66.7%, 9 events) reported ADRs in the NT-I7 120  $\mu\text{g}/\text{kg}$  group, 3 subjects (100.0%, 6 events) reported ADRs in the NT-I7 240  $\mu\text{g}/\text{kg}$  group, 2 subjects (66.7%, 8 events) in the NT-I7 480  $\mu\text{g}/\text{kg}$  group, 4 subjects (66.7%, 18 events) reported ADRs in the NT-I7 720  $\mu\text{g}/\text{kg}$  group, 2 subjects (66.7%, 4 events) reported ADRs in the NT-I7 960  $\mu\text{g}/\text{kg}$  group, 10 subjects (83.3%, 49 events) reported ADRs in the NT-I7 1200  $\mu\text{g}/\text{kg}$  group, and 2 subjects (100.0%, 16 events) reported ADRs in the NT-I7 1700  $\mu\text{g}/\text{kg}$  group (Table 11).

When the severity of ADRs was graded using the NCI-CTCAE (Version 4.0), 68 cases were mild (Grade 1), 43 cases were moderate (Grade 2), 5 cases were severe (Grade 3), and no ADR was reported as Grades 4 or 5. The most frequently reported ADRs were: injection site reaction (25 subjects, 71.4%, 61 events); pyrexia (12 subjects, 34.3%, 21 events); rash or rash papular (8 subjects, 22.9%, 9 events); fatigue, influenza like illness, and urticaria (each 4 subjects, 11.4%, 4 events); asthenia, pruritis, and decreased appetite (each 2 subjects, 5.7%, 2 events); and erythema, anaphylactic reaction, hypersensitivity, back pain, myalgia, nausea, and platelet count decreased (each 1 subject, 2.9%, 1 event). More details are provided in the NT-I7 Investigator's Brochure.

There were 10 AEs of special interest (AESI) as specified in the protocol in 5 subjects. The AESI included cases of potential drug-induced liver injury, conditions suggestive of autoimmune disorders, Grade 2 or higher AEs suggestive of hypersensitivity or immune-mediated reaction, Grade 2 or higher hypoxia or dyspnea, and Grade 2 or higher pleural effusion. One AESI (pneumonia) occurred in 2 subjects, all others were reported for a single subject (anaphylactic reaction, hypersensitivity, mesenteric arterial occlusion, pyrexia, hepatic failure, pleural effusion, urticaria, and hypotension).

One of 2 subjects at 1700  $\mu\text{g}/\text{kg}$  experienced DLT (hypersensitivity) as specified in the protocol. The RP2D and MTD of NT-I7 was determined to be 1200  $\mu\text{g}/\text{kg}$ .

Clinically significant changes in plasma and serum chemistry results after the administration of study drug were reported as AEs or were judged to be due to progression of the underlying disease.

The assessment of localized resistance of the injection site was made through patient interviews or observation of the injection site at each visit. The result of a localized resistance assessment determined clinically significant by the investigator was collected as an injection site reaction (ISR). A total of 61 ISRs occurred in 25 of 35 subjects (71.4%). The severity of all ISR AEs was Grade 1 or Grade 2.

Clinically significant results of physical examination and results of localized resistance assessment after the administration of the study drug were all reported as AEs, and no clinically significant results related to the study drug were found in other safety assessments such as vital signs, ECGs, and laboratory tests.

#### 10.1.2.3 Ongoing Study NIT-104/ABTC-103

A total of 261 TEAEs occurred in 12 of 12 (100%) total subjects. When the severity of AEs was graded using the NCI-CTCAE (Version 5.0), 151 TEAEs were mild (Grade 1), 74 TEAEs were moderate (Grade 2), 33 TEAEs were severe (Grade 3), and 3 TEAEs were life-threatening or required urgent intervention (Grade 4). There were 3 SAEs reported as seizure in 2 subjects (16.7%). One subject had 1 SAE of seizure that was considered unlikely related to NT-I7. A second subject had 2 SAEs of seizure that were both considered not related to NT-I7.

A total of 9 ADRs has occurred in 4 (3.3%) subjects. When the severity of ADRs was graded using the NCI-CTCAE (Version 5.0), 6 ADRs were mild (Grade 1), 2 ADRs were moderate (Grade 2), and 1 ADR was severe (Grade 3). No ADR was reported as Grade 4 or 5. The most common ADR was rash maculo-papular (28.6%). More details are provided in the NT-I7 Investigator's Brochure.

